Primary Objective: To compare medication adherence of solid organ transplant recipients, specifically liver and kidney transplants, using the mobile DOT (mDOT) application (i.e., intervention) to those who did not use the mDOT application (i.e., control). We will compare medication adherence between intervention and control arms using the Medication Level Variability Index (MLVI), a validated measure of adherence derived from the standard deviation of measured drug levels (22-23).

Secondary objectives:

- Clinical endpoints including rejection and hospitalization
- Patient reported adherence on immunosuppressant therapy instrument (ITAS)
- Patient-reported QoL outcomes as measured by PedsQL and SF-36
- Patient-reported self-efficacy using the Riekert Self-efficacy scale
- Patient-reported usability using the PSSUQ (treatment arm only)
- To examine the patterns of medication adherence in transplant recipients in both groups to better understand baseline medication adherence
- To understand the feasibility and acceptability of implementing such a system into the clinical workflow and patient follow-up care management

Design and Outcomes:

In this multi-center study, patients ≥ 13 years of age who receive a liver or kidney transplant at Johns Hopkins Hospital, University of Virginia Medical Center or University of Miami Medical Center will be recruited to participate in this randomized control trial (RCT).

There will be 2 arms participants may be randomly assigned to: intervention and control arms. Participants in the intervention arm will receive the mDOT application, and participants in the control arm will not. Both arms will still receive standard of care post-transplant.

We will use block randomization to assign participants to the intervention or the control group using random block sizes ranging from 2 to 8. Block randomization will improve the probability of balanced groups over the course of the study as well as during shorter time horizons. A research data analyst, blind to the group allocations, will generate a list of sequential group assignments using this method. The list will be used to create sequentially numbered, sealed envelopes that will be used to allocate consenting participants to the control or intervention arms of our study. Each patient will have a 50% chance to be in the intervention arm of the study.

Interventions and Duration:

Participants will be enrolled in the study for 12 months. All subjects will complete study assessments and have immunosuppressant levels and clinical outcomes followed for 12 months. Subjects randomized to the intervention group will use the app for the first 3 months following enrollment. Subjects randomized to the control group will not use the app and will follow routine standard of care.

No study visits are required of research participants after enrollment, but they will complete surveys and an interview over the phone.

Procedure	Baseline	3 months	6 months	9 months	12 months
Baseline clinical/demographic/lab info/baseline survey	X				
Immunosuppression levels and laboratory values collected from medical record	X	X	X	X	X
Interval health information collected		X	X	X	X
Patient-reported outcomes*	X	X			X
Phone Interview					X

*these include ITAS, PedsQL <18 years at enrollment or SF-36 if >18 years at enrollment, Reikert self-efficacy scale, PSSUQ (treatment arm only and only at 3 months)

Sample Size and Population:

Participant enrollment will continue until we have reached 25 participants in each arm by age (13-21 years and 22 years and older) for a total of 100 participants. We will follow all study participants for 12 months.

1. STUDY OBJECTIVES

1.1 Primary Objective

To compare medication adherence of solid organ transplant recipients, specifically liver and kidney transplants, using the mobile DOT (mDOT) application (i.e., intervention) to those who did not use the mDOT application (i.e., control). We will compare medication adherence between intervention and control arms using the Medication Level Variability Index (MLVI), a validated measure of adherence derived from the standard deviation of measured drug levels (22-23).

1.2 Secondary Objectives

- Clinical endpoints including rejection and hospitalization
- Patient reported adherence on immunosuppressant therapy instrument (ITAS)
- Patient-reported QoL outcomes as measured by PedsQL and SF-36
- Patient-reported self-efficacy using the Riekert Self-efficacy scale
- Patient-reported usability using the PSSUQ (treatment arm only)
- To examine the patterns of medication adherence in transplant recipients in both groups to better understand baseline medication adherence
- To understand the feasibility and acceptability of implementing such a system into the clinical workflow and patient follow-up care management

2. BACKGROUND AND RATIONALE

In adolescent and adult solid organ transplant recipients, poor adherence to immunosuppressant medications carries the risk of graft rejection, short- and long-term post-transplant complications, and increased healthcare costs (1-8). In transplant recipients, adherence to immunosuppressive drugs, as well as general medical indications is imperative to overall outcomes (9). The rate of non-adherence to immunosuppressive medications in transplant patients varies vastly, with reports ranging from 15-40% in adults and much higher at 50-70% among adolescents (9-14). Additionally, medication adherence is a key concern in the transition from adolescent to adult-centered transplant care, and transition planning should be prioritized in these transplant patients (15-18). Because of lacking objective and accurate non-adherence measurements, both to immunosuppressive drugs and medical indications, the true implications and prevalence of non-adherence is not yet well understood (19-21). Therefore, we believe that mobile health (mHealth) technology has the potential to allow clinicians and researchers to more comprehensively address and understand non-adherence in adolescent and adult transplant recipients.

emocha Mobile Health Inc. has developed an application that enables users to track dose-by-dose medication adherence through asynchronous, video directly observed therapy (DOT). This helps patients take their medication as prescribed and gives providers the assurance that their patients are supported and successful in treatment. DOT is the practice of watching a patient take every dose of medicine in-person, and has typically only been done in extreme cases because it can be both costly and burdensome: DOT is the standard of care for Tuberculosis treatment and has proven high-adherence rates. Through mHealth technology, DOT can be used more broadly and without added burden; emocha's technology allows this through enabling patients to use their mobile application

to view their regimen, record themselves taking every dose of their medication, report side effects or symptoms, visualize their treatment progress, and access educational content. This information is encrypted and transmitted to a HIPAA-secure web portal for providers to review. The aim of this study is to conduct a randomized control trial to compare medication adherence between patients who use the mHealth system against controls who do not.

emocha has formally evaluated their mDOT platform across several disease states: tuberculosis, Hepatitis C virus, and opioid use disorder. The U.S. Centers for Disease Control and Prevention (CDC) recognizes emocha's video modality as an acceptable form of DOT, according to their latest guidelines (24). To date, emocha has partnered with Johns Hopkins and three Maryland health department tuberculosis programs to assess quantitative, qualitative, and cost outcomes associated with emocha video DOT implementation. Among all participants – with more than 1,400 videos submitted thus far – mean patient adherence was 94 percent (median adherence 96 percent, interquartile range 93 to 100 percent). Similar adherence rates were proven in independent studies using emocha performed by Harris County, TX and the Puerto Rico Department of Health. Additionally, emocha is conducting a trial on the feasibility of video DOT for patients undergoing the initiation phase of buprenorphine treatment through office-based opioid treatment programs, as well as conducting ongoing research on Hepatitis C medication adherence among injection drug users.

3. STUDY DESIGN

The purpose of this study is to understand how the use of an mHealth application, mDOT, changes medication adherence behaviors among liver or kidney transplant recipients. For the purpose of this research, the mobile app is a device of non-significant risk and exempt from the IDE requirement. emocha Mobile Health is the device manufacturer.

In this multi-center study, patients ≥ 13 years of age who receive a liver or kidney transplant at Johns Hopkins Hospital, University of Virginia Medical Center or University of Miami Medical Center will be recruited to participate in this randomized control trial (RCT). There will be 2 arms participants may be randomly assigned to: intervention and control arms. Participants in the intervention arm will receive the mDOT application, and participants in the control arm will not. Both arms will still receive standard of care post-transplant.

Participants are followed for their compliance with standard of care recommendations. No additional care or procedures will be administered to study participants. Given the uncertainty in whether this mHealth intervention will improve rates of immunosuppression medication adherence in liver and kidney transplant recipients, a non-treatment group is necessary in order to identify whether an advantage exists.

4. SELECTION AND ENROLLMENT OF PARTICIPANTS

4.1 Inclusion Criteria

Participants must meet all of the following inclusion criteria to participate in this study:

- ≥ 13 years old
- Own a smartphone and are willing to receive information through it
- Received a liver or kidney transplant at a participating study site during or prior to the study period.

4.2 Exclusion Criteria

All candidates meeting any of the following exclusion criteria at baseline will be excluded from study participation:

- Patients with cognitive impairments will not be eligible for enrollment due to inability to provide informed consent.
- Inability or unwillingness of individual or legal guardian/representative to give consent.

4.3 Study Enrollment Procedures

Participants will be approached by the following methods:

For subjects ages 13-21 years old: either while they are an inpatient post-transplant or at any follow-up outpatient clinic visit by a study member to participate in this study.

For subjects >21 years old: either while they are an inpatient post-transplant or at their first post-op outpatient clinic visit by a study team member to participate in this study.

For all subjects:

When feasible to conduct in-person consenting, written consent will be obtained explaining the purpose of the study, their part in it, and that they can withdraw from the study at any time. As much time as necessary will be allowed for obtaining consent. Assent will be obtained from participants age 13-17 years, along with parental consent.

Additionally, we will make provisions for phone consent and enrollment if needed due to potential COVID-19 restrictions so that enrollment may proceed according to plan. If unable to conduct in-person consenting and enrollment process, patients will be contacted by phone and the study team will conduct the appropriate oral consent/assent procedures and conduct the procedures listed below remotely.

We will use block randomization to assign participants to the intervention or the control group using random block sizes ranging from 2 to 8. Block randomization will improve the probability of balanced groups over the course of the study as well as during shorter time horizons. A research data analyst, blind to the group allocations, will generate a list of sequential group assignments using this method. The list will be used to create sequentially numbered, sealed envelopes that will be used to allocate consenting participants to the control or intervention arms of our study. Each patient will have a 50% chance to be in the intervention arm of the study.

Participant enrollment will continue until we have reached 25 participants in each arm by age (13-21 years and 22 years and older) for a total of 100 participants and we will follow study participants for 12 months. No study visits are required of research participants after enrollment, but they will complete surveys and an interview over the phone.

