We will use block randomization to assign participants to the intervention or the control group using random block sizes ranging from 2 to 8. Block randomization will improve the probability of balanced groups over the course of the study as well as during shorter time horizons. A research data analyst, blind to the group allocations, will generate a list of sequential group assignments using this method. The list will be used to create sequentially numbered, sealed envelopes that will be used to allocate consenting participants to the control or intervention arms of our study. Each patient will have a 50% chance to be in the intervention arm of the study.

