5.2.2 Blinding

Research team members responsible for enrollment and reviewing emocha app submissions will not be masked to who is in the intervention or control arm. Patients will be aware of which arm they are randomized to as well. In this sense, the study will not be blinded to patients. Furthermore, patients/families will be strongly discouraged from discussing with their clinical team to which treatment arm they are enrolled. Data extraction (labs, drug levels) will be performed by study personnel that are blinded to the treatment arm. Individuals performing data analysis will receive de-identified data that does not explicitly describe which group is intervention and which is control, but simply the code without a key. Only the PI at each site and necessary personnel performing data extraction will have the key for the code to minimize bias in data analysis.

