9. STATISTICAL CONSIDERATIONS

Primary outcome variables:

12-week immunosuppression medication adherence:

We will measure medication adherence in both arms at 12 weeks. The Medication Level Variability Index (MLVI) will be used to analyze immunosuppression lab

values to determine adherence with a relative risk noted for standard deviation >2 .

Secondary outcome variables:

- Hospitalization days
- Biopsy-proven rejection
- Clinician-assigned rejection

We will recruit 100 liver and kidney transplant recipients (50/arm), and compare recipients who received the mHealth intervention to controls that did not receive it. The Medication Level Variability Index (MLVI) will be used to analyze immunosuppression lab values to determine adherence with a relative risk noted for standard deviation >2 . Descriptive statistics will be performed to compare frequencies of secondary outcomes (e.g., hospitalization, rejection, etc). Patient reported outcomes will be scored as appropriate and differences compared between treatment arms. Additionally, we will perform subgroup analyses for younger transplant recipients (age at transplant <40), older transplant recipients, men, and women.

In addition to understanding the efficacy of this technology in a transplant patient population, we will also evaluate the feasibility of implementing such a system into clinical workflow. We will examine time spent by reviewers each week using mDOT, most ideal time post-transplant to consent and educate participants on using the application, and streamlining the workflow involved in the application. In order to ensure acceptability among the patients who will be using the app, we will survey all participants in the intervention arm at the end of the study period on their overall satisfaction in using the app. This survey will be administered with the ITAS scale over the phone. In addition, we will also examine consent rate and use of the mDOT app by participants over time to understand acceptability of using the application.

Feasibility will also be measured through phone interviews with all study participants at 12 months. We will contact all patients who consented to be in the study to participate in the phone interviews. The interviews will be semi-structured, with a set of pre-written questions as the guide. All interviews will be audio recorded. Transcription of the interviews will be conducted by Production Transcripts, Inc.

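### Enrolment aims for 25 per arm in each of two age groups, but no age strata are stated for the block list and the analysis ignores those groups

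*Combined protocol and SAP*

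**What the plan says.** Enrolment is defined by four cells. Section 4.3 states: "Participant enrollment will continue until we have reached 25 participants in each arm by age (13-21 years and 22 years and older", and the same sentence continues "for a total of 100 participants". The opening summary, under Sample Size and Population, repeats this. Section 9 restates only the total of 100, with 50 per arm.

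Randomisation is described in the same words in the opening summary (Design and Outcomes), Section 4.3 and Section 5.2.1. Blocks are of random size from 2 to 8, and an analyst "will generate a list of sequential group assignments using this method". Section 5.2.1 then says: "The list will be used to create sequentially numbered, sealed envelopes". No stratification by age, site or organ is named.

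In Section 9 the primary comparison uses MLVI "with a relative risk noted for standard deviation >2", with no mention of age. The planned subgroups are "subgroup analyses for younger transplant recipients (age at transplant <40), older transplant recipients, men, and women". The enrolled groups, 13-21 and 22 and older, do not appear in the analysis.

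Section 2 gives non-adherence as "15-40% in adults and much higher at 50-70% among adolescents".

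**The concern.** A single blocked list keeps the arms close to equal overall but does not control the split within an age group. If one list is used, the target of 25 per cell and the total of 100 will usually not be met together. The plan does not say which gives way.

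The analysis raises the larger question. The trial recruits deliberately by age, and its own background section reports non-adherence that differs sharply between adolescents and adults. Age group is therefore expected to predict the outcome, and leaving it out of the primary comparison gives up precision that costs nothing to keep.

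The cut at 40 does not fill the gap. Everyone aged 13-21 at enrolment was transplanted before 40, so they are pooled with any adults transplanted before 40. The 50 participants recruited as adolescents and young adults have no planned estimate of their own.

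**Working it through.** **1. The plan's total.** 25 per cell x 2 arms x 2 age groups = 100, or 50 per arm. This agrees with the opening summary and Sections 4.3 and 9.

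**2. What a single list delivers.** Simulation of 20,000 trials per age mix. Assumptions, not given in the documents: 30%, 50% or 70% of arrivals are aged 13-21, and block sizes 2, 4, 6 and 8 are equally likely.

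| Share aged 13-21 | 30% | 50% | 70% |
|---|---|---|---|
| *Each age group closed at 50* | | | |
| All four cells exactly 25 | 15.3% | 12.4% | 14.8% |
| Smallest cell 22 or fewer | 22.8% | 32.8% | 23.2% |
| Mean stratified variance relative to 25/25 | 1.0065 | 1.0099 | 1.0066 |
| *Each age group open until both arms reach 25* | | | |
| Mean total N | 105.3 | 106.8 | 105.2 |
| 90th percentile of N | 112 | 116 | 112 |
| N exactly 100 | 15.0% | 12.7% | 15.2% |

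Analytic check: if the arms are exactly 50/50 overall and each age group has 50, the number of one age group in one arm is hypergeometric(100, 50, 50). This gives 15.8% for an exact 25/25 split and 31.7% for 28/22 or worse, in line with the simulation.

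**3. Cost of the imbalance alone.** For 28/22 in both age groups: (1/28 + 1/22)/(2/25) = 1.0146, a variance increase of 1.5%. The simulated average is 0.7-1.0%.

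**4. Gain from adjusting for age group.** The event rates are stand-ins, the midpoints of Section 2's ranges: 60% for adolescents and 27.5% for adults. They are not rates of MLVI above 2. No treatment effect is assumed.

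- Unadjusted: pooled rate (0.60 + 0.275)/2 = 0.4375; SE = sqrt(2 x 0.4375 x 0.5625/50) = 0.0992.
- Stratified, 25/25 cells: variance = 0.25 x (2 x 0.60 x 0.40/25 + 2 x 0.275 x 0.725/25) = 0.00879; SE = 0.0937.
- Variance ratio: 0.00879/0.00984 = 0.893, a reduction of 10.7%.
- Stratified, 28/22 cells: SE = 0.0944, a reduction of 9.4%.
- Ends of the ranges: 50% v 40% gives a reduction of 1.0% (at 28/22 a rise of 0.4%); 70% v 15% gives a reduction of 30.9%.

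The log Mantel-Haenszel relative risk shows the same ratio. Unadjusted variance is 2 x 0.5625/(50 x 0.4375) = 0.0514. The stratified variance is 12.5 x (0.24 + 0.1994)/(12.5 x 0.875)^2 = 0.0459. The ratio is 0.893.

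**5. How much comes from adjustment alone, keeping one list.** (1 - 0.8927 x 1.0065)/0.1073 = 0.95 and (1 - 0.8927 x 1.0099)/0.1073 = 0.92. So 92-95% of the gain at the midpoints needs no change to the lists.

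**6. Precision within an age group, 25 v 25.** The half-width is 1.96 x sqrt(2q(1-q)/25). For 13-21, q of 0.50 to 0.70 gives 27.7 to 25.4 points. For 22 and older, q of 0.15 to 0.40 gives 19.8 to 27.2 points.

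**The case against.** The strongest reply is that the first part is a gap in wording. A target of 25 per arm by age is most naturally met with age-specific lists, and one sentence would say so. Every shortfall figure above depends on the opposite reading. The enrolment sentence can also be read as a stopping rule on the cells, with 100 merely their sum. Even on a single list the harm is about 1% in variance, or five to seven extra participants. All of this stands. The list alone would be a minor clarification, and missing exactly 25 in a cell is not a serious defect.

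The gain from adjustment can also be disputed. Section 2 summarises general non-adherence in adolescents and adults. It does not give MLVI rates at 12 weeks and does not use the cut at 21/22. The gain runs from almost nothing to 31%, and the unadjusted randomised comparison is valid. So the size is uncertain. The direction is not in much doubt, since the plan itself expects the outcome to differ by age and the adjustment uses a variable already collected.

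Thirdly, separate results by age group will be imprecise, and the groups differ in more than age. Section 4.3 recruits ages 13-21 at any follow-up visit but older participants only as inpatients or at the first post-operative visit. A contrast between the age groups therefore mixes age with time since transplant. This limits how those results may be read. It does not affect adjustment of the primary comparison.

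**Conclusion.** The concern holds. The cell target and the randomisation text are not joined by any stated stratification, and Section 9 makes no use of the groups by which the trial enrols.

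The allocation part is small: random error rather than bias, costing 0.7-1.0% in variance on average if one list is used, under the assumed age mixes and block sizes. The analysis part matters more. At the stand-in midpoint rates, adjustment reduces the SE of the risk difference from 9.9 to 9.4 points (variance down about 11%, range 1% to 31%). The absence of strata and of age adjustment is certain from the text; the size of the gain rests on rates that the documents do not give for MLVI. It is worth fixing because the better analysis is nearly free.

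**What to change.** 1. **Lists.** State that randomisation uses separate block lists and envelope series for 13-21 and for 22 and older, each closing at 50. Keep the random block sizes, cut the last block at 50 and accept a cell of 24 or 26. In simulation the smallest cell is then at least 24 in 99.5% of trials and never 22 or fewer, and all four cells are 25 in 56.9%. Do not force exactly 25:25. Section 5.2.2 says "Research team members responsible for enrollment and reviewing emocha app submissions will not be masked"; if complete blocks had to total 50, running counts would make the last 1.35 allocations per age group certain on average (at most 4). If envelopes are held by site, use six site-by-age series with the same cap. The smallest cell is then at least 24 in 82-83% of trials and 22 or fewer in 1.1%, though all four cells are exactly 25 in only about 19% (half of arrivals aged 13-21, sites 60/20/20).

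2. **Primary analysis.** Adjust the MLVI comparison for enrolled age group, for example with a Mantel-Haenszel relative risk for a standard deviation above 2. This gives nearly all of the gain whatever is done about the lists.

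3. **Age-group results.** Report 13-21 and 22 and older beside the cut at 40, as estimates with confidence intervals and not as tests. Note that differences between the groups may reflect time since transplant.

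**Cost.** One extra envelope series (or six in all if held by site), a short amendment and no extra patients. The final allocations become slightly more predictable because each age group has a known end. If enrolment has begun, use the new lists for the remaining participants and settle the analysis changes before anyone sees unblinded data; close cell balance is then not guaranteed.
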